5.4.1.5 Baseline characteristics on COVID-19 infection (for subjects in Group 2A-2D only)

- COVID-19 related symptoms (presence/absence)
- Nasopharyngeal / Oropharyngeal swab CT values as well as copies/ml

5.4.2 Compliance

Compliance will be evaluated by whether or not the medication was administered according to protocol.

5.4.3 Exposure

Total dose of specific trial medication [mg]:

Total dose of trial medication will be calculated separately for DZIF-10c, and the matching placebo. It will be based on the actual dose [mg] received. Total dose will be evaluated descriptively.

Dose intensity of specific trial medication [%]:

For each formulation (inhaled or i.v.) dose intensity of trial medication will be calculated separately for DZIF-10c, and the matching placebo.

$$\text{Dose intensity [%]} = \frac{\text{Total dose of specific trial medication actually received by a subject}}{\text{Planned total dose of specific trial medication}} \times 100$$

The planned total dose is calculated as the total dose of the medication a subject should have received based on their baseline weight and the dose level of the treatment cohort they were assigned to. Dose intensity will be summarised in percent and in categories ($\leq 50\%$, $> 50\% - \leq 90\%$, $> 90\% - < 100\%$, 100%) and evaluated descriptively.

Inhalation volume [ml]:

The total inhalation volume received by a subject during the complete inhalation duration. Inhalation volume will be evaluated descriptively.

Infusion volume [ml]:

The total infusion volume received by a subject during the complete infusion duration. Infusion volume will be evaluated descriptively.

Time to premature inhalation stoppage in classes:

The following classes will be used: $\leq 5\text{min}$, $> 5 - \leq 10\text{ min}$, $> 10\text{min}$

Time to premature inhalation stoppage will be evaluated descriptively.

Time to premature infusion stoppage in classes:

The following classes will be used: $\leq 5\text{min}$, $> 5 - \leq 15\text{ min}$, $> 15 - \leq 30\text{ min}$, $> 30\text{min}$

Time to premature infusion stoppage will be evaluated descriptively.

5.4.4 Liver function tests

Time to initial onset of liver enzyme elevations and frequency of patients with liver function test abnormalities will be produced. A listing of all liver function tests will be provided for all subjects who meet the following criteria at any time:

- ALT or AST $\geq 3 \times \text{ULN}$ and elevation of total bilirubin $\geq 2 \times \text{ULN}$ at the same time

In addition, E-dish plots may be used for ALT and AST.

5.4.5 Marked changes in vital signs

A marked increase is defined as:

- Systolic Blood Pressure $> 150 \text{ mmHg}$ and increase $\geq 25 \text{ mmHg}$ above baseline
- Diastolic Blood Pressure $> 90 \text{ mmHg}$ and increase $\geq 10 \text{ mmHg}$ above baseline
- Pulse Rate $> 100 \text{ bpm}$ and increase $\geq 10 \text{ bpm}$ above baseline

A marked decrease is defined as:

- Systolic Blood Pressure $< 100 \text{ mmHg}$ and decrease $> 10 \text{ mmHg}$ below baseline
- Diastolic Blood Pressure $< 60 \text{ mmHg}$ and decrease $> 10 \text{ mmHg}$ below baseline
- Pulse Rate $< 60 \text{ bpm}$ and decrease $> 10 \text{ bpm}$ below baseline

6. GENERAL ANALYSIS DEFINITIONS

6.1 TREATMENTS

Please see CTP Sections 5.9.1 and 5.9.2 for information on treatments as well as administration. Assignment of subjects to treatment groups can be found in CTP Section 5.9.4, and Section 5.9.5 contains information on the selection of doses.

Note: the last day of each of the periods is excluded from the respective period. It defines the first day of the subsequent period.

[figure not shown]
- Screening:
 - Phase I part (Groups 1A-1C, 2A-2C): From informed consent to trial drug intake
 - Phase IIa part (Group 2D): From informed consent to randomisation
- Post-randomisation (if applicable^{[a][b]}):
 - From randomisation to trial drug intake in treatment period
- Treatment period:
 - From date of trial drug intake to date of trial drug intake plus one day
- Residual effect period:
 - From the date of trial drug intake plus one day to 90 days plus one day after trial drug intake
- Post-study^[a]:
 - From 90 days plus one day after trial drug intake or date of intake of other SARS-CoV-2 medication, whichever occurs earlier

^[a] This period is optional insofar as it does not necessarily exist for all subjects.

^[b] This period is only applicable for subjects in the phase IIa part of the trial.

Please see [Figure 6.1: 1](#) below for a graphical depiction of the individual treatment periods. The grey highlighted areas are the optional periods that do not necessarily exist for all subjects.

All analyses will be based on the actual treatment the subjects received unless stated otherwise.

- [1] The orange area represents the screening period, the green area the treatment period, and the blue area the residual effect period.
- [2] This grey area represents the optional post-randomisation period. It is only applicable for subjects in the phase IIa part of the trial and, hence, does not necessarily exist for all subjects. Ideally, date of randomisation and date of treatment start are on the same day.
- [3] This grey area represents the optional post-study period. It does not necessarily exist for all subjects.

Figure 6.1: 1 Period overview for a participant of study Uni-Koeln-4370 / BI Trial 1487-0005.

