## 5.6. Follow-up Visits

Participants will be followed for a total of 90 days (+/- 7 days) after trial drug administration.

At these follow-up visits, trial staff will

- Review the interim medical history including concomitant medication
- Review safety laboratory results
- Perform symptom-directed physical exams
- Perform procedures and obtain samples as outlined in the Visit Schedule (**Appendix II**)

For SARS-CoV-2-infected individuals, trial visits may be conducted at home during the period of quarantine. Trial visits on days 5 and days 10 are considered optional for SARS-CoV-2-infected individuals in quarantine.

In healthy volunteers (**Groups 1A-1C**), an optional visit at day 5 may be included to facilitate denser PK sampling.

Should trial participants become hospitalized during the follow-up phase, the visit schedule should be followed as possible.

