#### **5.9.7. Previous and Concomitant Medication**

Following trial drug administration, the standard of care may be provided as required by the medical condition and deemed appropriate by health care providers.

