7.8.1 Adverse Events

Unless otherwise specified, the analyses of adverse events (AEs) will be descriptive in nature. All analyses of AEs will be based on the number of subjects with AEs and NOT on the number of AEs.

For analysis multiple AE occurrence data on the eCRF will be collapsed into an AE provided that all of the following applies:

- All AE attributes are identical (LLT, intensity, action taken, therapy required, seriousness, reason for seriousness, relationship, outcome, AESI and CTCAE grade (based on version 5)).
- The occurrences were time-overlapping or time-adjacent (time-adjacency of 2 occurrences is given if the second occurrence started on the same day or on the day after the end of the first occurrence).

The analysis of AEs will be based on the concept of treatment emergent AEs. That means that all adverse events occurring after drug intake until the end of the residual effect period (+90 days thereafter) (+7 and +28 days as additional analysis) will be assigned to the treatment. In addition, AEs starting from day 9 until day 91 will be tabulated separately. All adverse events occurring before drug intake will be assigned either to 'screening' or 'post-randomisation' (phase IIa part and for listings only). All adverse events occurring after drug intake +90 days will be assigned to 'post-study' (for listings only). For details on the treatment definition, see [Section 6.1](#).

Adverse events related to infusion-related reactions (AEs presenting as hypersensitivity/allergic reaction, anaphylaxis, or cytokine release syndrome) as well as inhalation-related reactions presenting as allergic reaction (e.g., bronchospasm that may manifest with wheezing and/or respiratory distress) will be considered as protocol-specified AESIs, and ticked as such in the eCRF. Further adverse event groupings by safety topic have been defined outside the trial protocol, which will be continuously updated at project level (2). These safety topics are deemed of particular importance, and these definitions can be based on selection of coded terms

based on MedDRA. The latest approved version of the project level overview archived prior to either DBL will be used in the corresponding CTR.

An overall summary of adverse events having occurred during trial participation will be presented, including all AEs occurring:

- Within the first 7 days after drug administration
- Within the first 28 days after drug administration (sensitivity analysis)

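### SAP 6.1 starts the post-study period at intake of other SARS-CoV-2 medication, which contradicts its own residual effect period and the adverse event rule in SAP 7.8.1

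*SAP*

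**What the plan says.** SAP 6.1 divides each participant's time into consecutive periods. The residual effect period runs "From the date of trial drug intake plus one day to 90 days plus one day after trial drug intake". The post-study period runs "From 90 days plus one day after trial drug intake or date of intake of other SARS-CoV-2 medication, whichever occurs earlier". A note in the same section says that "the last day of each of the periods is excluded from the respective period. It defines the first day of the subsequent period".

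SAP 7.8.1 bases the AE analysis on treatment-emergent events and assigns to treatment "all adverse events occurring after drug intake until the end of the residual effect period (+90 days thereafter"). It continues: "All adverse events occurring after drug intake +90 days will be assigned to 'post-study' (for listings only"). It does not mention other medication, but it sends the reader to 6.1 for the treatment definition.

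Three other SAP sections depend on the same periods. Section 6.6.1 defines on-treatment as the treatment period plus the residual effect period. The date-imputation note in 9.4 uses the end of the residual effect period. Section 7.2.2 uses that end to separate on-treatment therapies from post-study drug discontinuation therapies. None of the three names a medication trigger.

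Protocol 8.1.3 evaluates safety events up to the day 7 visit, from then to the end of study, and in aggregate. Protocol 5.9.7 says that after dosing "the standard of care may be provided as required by the medical condition".

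**The concern.** For a participant who takes other SARS-CoV-2 medication before the residual effect period is over, SAP 6.1 places the same days in two periods. The medication clause has no evident purpose unless it ends the residual effect period early. A programmer who follows the reference from 7.8.1 to 6.1 could reasonably apply it that way.

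The cut would then depend on outcome. Protocol 4.1.2 says that guidelines did not recommend specific antiviral medication for this population at baseline, and Protocol 1.1 describes the evidence for remdesivir and dexamethasone in hospitalised patients needing oxygen. Later use of such drugs therefore plausibly marks deterioration. This is an inference from the documents, which do not state it. Disease enhancement is a named risk in Protocol 4.2.1 and safety is the primary objective, so later serious and fatal events in participants who deteriorate are the ones the main safety tables most need to keep.

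Timing adds to this. Group 2D is unblinded for the analysis after the day 7 visit (Protocol 8.1), so a choice between the two readings made after that point would be made with treatment assignments known.

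**Working it through.** **1. The periods without the medication clause.** Let t be days after drug intake. By the note in SAP 6.1, the closing day of a period belongs to the next one.
- Treatment period: t = 0.
- Residual effect period: t = 1 to 90 (t = 91 is excluded).
- Post-study: t = 91 onwards.

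SAP 7.8.1 assigns to post-study what occurs after +90 days, which is also t = 91 onwards. Without the clause, 6.1 and 7.8.1 agree to the day.

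**2. The periods with the clause.** Suppose the other medication is taken at t = m, with m between 1 and 90. The residual effect period still covers t = 1 to 90, but post-study now covers t = m onwards. The overlap is 90 − m + 1 = 91 − m days: 90 days if m = 1, and 1 day if m = 90. The contiguity note allows no overlap, so the two definitions cannot both hold.

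**3. Which outputs depend on the choice.**

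| Output | Defined by | If 7.8.1 governs | If the 6.1 clause governs |
|---|---|---|---|
| Treatment-emergent tables by system organ class and preferred term; serious, drug-related and fatal AE tables (7.8.1) | Residual effect period | AEs from m to 90 tabulated | AEs from m onwards in listings only |
| Concomitant therapies (7.2.2) | End of residual effect period | Therapies started after m, up to 90, are on-treatment | They become post-study drug discontinuation therapies |
| 7-day primary analysis (5.1, 7.4.1) | Onset within 7 days | Included | Not affected as written |
| Day 9 to day 91 tables and any-time summaries (7.4.2, 7.8.1) | Onset time | Included | Not affected as written |
| Whole-trial repeats of the safety outputs (9.1.1.3, 9.1.2.3) | Trial duration | Included | Not affected as written |

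**4. Comparison with the protocol.** Protocol 8.1.3 has no cut at other medication. SAP 4.1 cites its sentence on time periods and only adds outputs to it. SAP 4.2, which lists changes from the protocol, declares no cut.

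**5. Size.** Protocol 8.2 gives 90% intervals for an AE rate in an arm of 20. They reproduce with p ± 1.645·√(p(1−p)/20):
- 20%: 5.3 to 34.7 (stated 5 to 35)
- 25%: 9.1 to 40.9 (stated 9 to 41)
- 30%: 13.1 to 46.9 (stated 13 to 47)

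No stated figure is wrong. For any event type, a participant whose only such event starts after the medication lowers the arm's proportion by 1/20 = 5 points. For example, 5/20 = 25% becomes 4/20 = 20% with one such participant and 3/20 = 15% with two. The documents give no frequency of such medication. If it is assumed that one arm loses 0 to 3 more participants than another, the apparent difference shifts by 0 to 3/20 = 15 points. The matching yardstick is the 90% half-width for a difference between two arms at 20% each: 1.645·√(2 × 0.16/20) = 20.8 points. The single-arm half-width, 1.645·√(0.16/20) = 14.7 points, is not the right comparison for a difference.

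**The case against.** The strongest reply is that the operative rule is in 7.8.1, not 6.1. Section 7.8.1 uses time alone; the residual effect period in 6.1 has a fixed end; 6.6.1 and 9.4 follow it. One clause stands against all of these. On that reading nothing moves, and the clause is a leftover. This stands to the extent that a reader who infers that the SAP does remove these AEs goes further than the text. It does not remove the defect, because 7.8.1 defers to 6.1 for detail and 6.1 does not agree with itself. The period diagram, Figure 6.1: 1, is not reproduced in the text reviewed here, so it cannot settle the matter.

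Other stronger readings are also unsupported:
- **The primary window is affected.** SAP 7.4.1 takes every AE with onset in the first 7 days, with no condition on other medication.
- **The events vanish from all counts.** The any-time summaries and the day 9 to day 91 tables are defined by onset time, and safety events are also listed by participant.
- **The overall AE proportion would shift markedly.** Worsening of COVID-19 is itself an AE (Protocol 9.1.1). It would usually start before the medication it prompts and keep the participant in the numerator. Later serious or fatal events are more exposed than the proportion with any AE.
- **Any medication, or a vaccine, triggers the cut.** The SAP says other SARS-CoV-2 medication and does not define it. SAP 9.3 groups corticosteroids, monoclonal antibodies, anti-infectives, vaccines and blood products without saying which would count.
- **The AE period must run to the last visit.** Protocol 5.6 allows a final visit up to 90 + 7 = 97 days after dosing ("Participants will be followed for a total of 90 days (+/- 7 days) after trial drug administration"). Whether to tabulate AEs after day 90 is a separate choice, and this contradiction can be resolved without it.

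**Conclusion.** SAP 6.1 is wrong as written. Its post-study definition contradicts its residual effect period, its contiguity note and SAP 7.8.1, and it opens the way to a cut that Protocol 8.1.3 does not contain and SAP 4.2 does not declare. If the clause is programmed, the treatment-emergent tables lose AEs, including serious and fatal ones, after an event that plausibly marks deterioration and may differ by arm. Therapies are also reclassified under 7.2.2.

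The conclusion that the text is contradictory rests on wording alone. The conclusion that the cut would be informative rests on the inference that such medication follows worsening. The size is unknown: 5 points per affected participant in an arm of 20 is conditional arithmetic, not an estimate. The analyses are descriptive and the primary analysis is untouched as written. The case for acting is that the main safety tables should not depend on how a programmer resolves the conflict.

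**What to change.** In SAP 6.1, end the post-study definition at its 90-day limb for AE assignment, and strike the alternative trigger (intake of other SARS-CoV-2 medication) together with the words that take the earlier of the two dates. Section 6.1 then agrees with 7.8.1, 6.6.1 and 9.4, and AEs through the residual effect period are tabulated whatever other medication is taken. The therapy categories in 7.2.2 follow without further change. Check that Figure 6.1: 1 shows the same periods.

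If the team wants to see AEs before such medication, add one table labelled as supplementary, and define the term by stating which drug classes count, including whether vaccines do.

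The cost is one clause in the SAP and at most one extra table. No new data are needed. Since version 2.0 is described as final, the change needs a short amendment or a dated clarification before the final tables are programmed.

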##### Randomized Placebo-Controlled Phase (Group 2D)

The primary dataset for analysis is the safety population (as treated). This population includes all trial subjects who received any amount of the study drug.

The secondary dataset for analysis is a modified intention-to-treat (mITT) population. This dataset includes all randomized trial participants receiving study drug inhalation and infusion and who have at least a baseline (day 0) value and a second measurement of viral RNA shedding in nasopharyngeal swabs by qRT-PCR up to the day 7 visit. The evaluation is carried out strictly in accordance with the allocation by randomization.

Additional analysis populations can be defined in the SAP.

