#### **8.1.4. Secondary and Exploratory Outcomes and Target Variables**

Analysis is descriptive in nature. Secondary and exploratory endpoints will be evaluated by dose or treatment group and visit. Endpoints will be evaluated mainly in the safety population (dose escalation phase) or in the mITT population (**Group 2D**). Figures may show development over time where sensible. Endpoints can additionally be analysed by suitable multivariable models, including covariates. Substitution of missing values is not planned; the main efficacy analysis of time weighted average change of viral RNA shedding is possible in the mITT without substitutions. Complete methods will be specified in the SAP.

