6.2 IMPORTANT PROTOCOL DEVIATIONS

No per protocol set analysis will be performed for this study; however, the following list in [Table 6.2: 1](#) defines the different categories of potentially important protocol deviations (iPD), and it shows whether subjects will potentially be excluded from evaluations performed in this trial. The proportion of subjects with potential iPDs will be presented for completeness purposes and to demonstrate the adherence to the CTP.

Table 6.2: 1 Handling of iPDs

iPD code	iPD Category & Brief Description	Excluded from which analysis set
A	In/Exclusion Criteria not met	
A1	Inclusion Criteria not met	
A1.1	SARS-CoV-2-RNA negative (SARS-CoV-2-uninfected subjects)/positive (SARS-CoV-2-infected subjects) naso- or oropharyngeal swab obtained within 3 calendar days before study drug administration by NAAT	None
A1.2	SARS-CoV-2-infected subjects only: Onset of COVID-19 symptoms not within 7 days prior to study drug administration or No non-reactivity of serum or plasma antibodies against SARS-CoV-2 by serological assay at screening	None
A2	Exclusion Criteria not met	
A2.1	Subjects with laboratory values that indicate additional risk	None
A2.2	Patient with other underlying diseases, conditions or risks which are excluded as per clinical trial protocol	None
A2.3	Forbidden previous therapy as per clinical trial protocol	None
B	Informed Consent	
B1	Informed consent not available/not done	All
B2	Informed consent too late	None
C	Trial Medication and Randomisation	
C1	Wrong dose level received compared to dose level subject was assigned (phase I) / randomised (phase IIa) to	None
C2	Medication taken that is not matching the treatment a subject was randomised to (phase IIa only)	None
E	Missing data	

E1	No negative pregnancy test result prior to / and the end of study participation	None
E2	Missing diary data for 7 consecutive days within the first 14 days	None
F	Study Procedure Timing	
F1	Time window violation for drug administration (drug administration \leq 3 days after screening)	None
F2	Time window violation for procedures performed post baseline within the first 7 days (day 1 and day 2 without time window; day 4 within +/- 1 day; day 8 +/- 2 days)	None
G	Other Trial Specific Important Violation	
G1	Other protocol violations affecting patient rights or safety (manual PVs to be captured)	None

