6.3 SUBJECT SETS ANALYSED

- Screened set (SCS):
 - This subject set includes all subjects having signed informed consent and would correspond to the intention-to-treat set (ITT) in the phase I part of the trial.
- Randomised set (RS):
 - This subject set includes all randomised subjects in the phase IIa part of the trial, whether treated or not. This would correspond to the intention-to-treat set (ITT) in the phase IIa part of the trial
- Treated set (TS):
 - This subject set includes all subjects who received any amount of study drug.
- Modified Treated set (mTS):
 - This subject set includes all subjects who received any amount of study drug and did not require replacement in the phase I part of the trial. Details about requirement for replacement can be found below.
- Modified Intention-To-Treat set (mITT):
 - This subject set includes all randomised subjects in the phase IIa part of the trial that received any amount of study drug and who have at least a baseline value and a second measurement in the first week (up to 7 days after drug intake) of viral RNA shedding in nasopharyngeal swabs by qRT-PCR.

- PK parameter analysis set (PKS):
 - This subject set includes those subjects in the TS with at least one valid serum concentration of DZIF-10c available

Participants who are withdrawn from the trial after DZIF-10c administration will not be replaced, except for participants during the dose-escalation phase of the trial that are not followed until at least the day 7 visit after drug administration for reasons not related to safety events. Subjects who were replaced will be excluded from the primary analysis of the primary endpoint. Replacement of subjects will be determined on a case-by-case basis; exclusion of these subjects from the primary analysis will be confirmed by the trial team at the report planning meeting prior to database lock.

Please see [Table 6.3: 1](#) for a general overview which patient set will be used for which type of analyses. Additionally, biomarker analyses might be performed on subsets of the mITT set.

Table 6.3: 1 Subject sets used in the different types of analysis

Type of analysis	Subject set					
	SCS	RS	TS	mTS	mITT	PKS
Primary endpoints			X		X ^[1]	
Further endpoints				X		
Safety data, ADA & treatment exposure				X		
Demographic/baseline characteristics				X		
Disposition		X	X			
PK parameters						X
Viral Load				X ^{[1][2]}	X	

^[1] Will be used for the phase I part of the trial.

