7.5.2.2.2 The frequency and magnitude of anti-drug antibodies targeting DZIF-10c

The same assessments will be performed as described in [Section 7.5.2.1.2](#).

This endpoint will be evaluated on the subject set TS.

7.5.2.2.3 SARS-CoV-2 RNA shedding in nasopharyngeal swabs determined by qRT-PCR in SARS-CoV-2-infected individuals

All evaluations for the first 7 days after drug administration will be done on the mITT set and will take data into consideration based on the time window around the corresponding visit as defined in [Section 6.7](#). The latest day to be taken into account is 7 days after drug administration. The evaluations for the later time points will be based on all subjects in the subject set TS who have at least a baseline value and a second measurement in the respective time period of viral RNA shedding in NP swabs by qRT-PCR.

Absolute viral load in SARS-CoV-2-infected individuals, as well as absolute and relative changes from baseline, will be summarised descriptively for each assessment time point and plotted by treatment arm and listed.

Time-weighted average change in viral load

The evaluation of viral load will be done by a time-weighted average change in \log_{10} viral load from baseline, defined by:

$$\frac{\sum_{i=a}^{b-1} \{0.5 * (Y_i + Y_{i+1}) * (t_{i+1} - t_i)\}}{(t_b - t_a)}$$

where

- Y_i = change from baseline in \log_{10} viral load at visit i
- t = time at the specified time point (the actual study day)
- a = baseline assessment at day 1
- b = last assessment at or prior to the threshold day (7 days after drug intake)

A parametric analysis of covariance (ANCOVA) model with corresponding baseline viral load and antibody status will be used. Adjusted means and 95% confidence intervals (CIs) will be provided. Missing values will not be imputed and since a linear trajectory on the log scale is expected, the normalisation by the denominator assures comparability of the values if t_b is different between patients.

Ratios between means (DZIF-10c vs placebo) will be calculated for each treatment arm separately for the respective time period. These calculations will be based on the mean time-weighted average change in viral load based on the ANCOVA model. CIs for the ratios will be reported for which the Delta method (Taylor method) will be used to calculate the variance of the ratios.

Mixed effect Model for Repeated Measures (MMRM)

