7.6.2.5 Time to resolution of self-assessed SARS-CoV-2-related symptoms

A log-rank test will be used to evaluate the effect of DZIF-10c on time to resolution of self-assessed SARS-CoV-2-related symptoms compared to Placebo over 29 days. A Cox proportional-hazards model will be used to derive the hazard ratio and 95 % CI between each of the two randomised treatment regimens that were assigned DZIF-10c and the placebo regimen (Hazard ratios <1 will favour DZIF-10c). This will be done for each symptom (cough, feverishness, body ache, headache, sore throat, shortness of breath, loss of taste or smell) separately as well as together for all symptoms. Breslow's method for handling ties will be used. Kaplan-Meier plots by treatment group will also be presented and the rates at day 29 compared.

This endpoint will be evaluated on subjects from the subject set TS.

7.6.2.6 Differences of viral spike gene sequences obtained before and after study drug administration and the investigation of the effect of observed mutations on viral sensitivity to DZIF-10c in neutralization assays

These analyses will be performed by UKK and reported in a separate report which will be appended to the CTR.

7.6.2.7 The activity and frequency of SARS-CoV-2-reactive immune cells following DZIF-10c administration

As described in Section 4, these analyses will be performed by UKK and will not be included in the CTR but might be reported elsewhere.

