9.2.1 Change from baseline

9.2.1.1 Time-weighted average change in viral load

Change from Baseline in Viral load:

```
#####
%MACRO auc (idvar =, dsname =, timevar =, yvar =, resultds =);
  %LOCAL lastid;
  %* All data manipulations are to be made outside of the macro;
  %* Sort dataset -> 1st data point is the starting point;
  PROC SORT DATA = &dsname OUT = _tmp;
    BY &idvar &timevar;
  RUN;

  %* Get last idvar;
  DATA _null_;
    y = COMPBL ("&idvar");
    y1 = COMPRESS (y);
    n = LENGTH (y) - LENGTH (y1);
    CALL SYMPUT ('lastid', COMPRESS (PUT (n+1, 5.)));
  RUN;

  %PUT lastid = &lastid;
  %LET lastvar = %SCAN (&idvar, &lastid, %STR ( ));

  DATA _tmp1;
    SET _tmp;
    RETAIN _ltime _lyvar _difftime _mintime;
    BY &idvar;
```

```

IF FIRST.&lastvar THEN DO;
  _ltime = &timevar;
  _lyvar = &yvar;
  _difftime = .;
  _mintime = &timevar;
END;
IF NOT FIRST.&lastvar THEN DO;
  auccomp = 0.5 * (&yvar + _lyvar) * (&timevar - _ltime);
  diff = (&yvar - _lyvar);
  difft = (&timevar - _ltime);
  _ltime = &timevar;
  _lyvar = &yvar;
  IF last.&lastvar THEN _difftime = &timevar - _mintime;
  OUTPUT;
END;
RUN;

PROC SUMMARY DATA = _tmp1;
BY &idvar;
VAR auccomp;
OUTPUT OUT = &resultds._pre SUM = auc;
RUN;

DATA &resultds;
MERGE &resultds._pre _tmp1 (WHERE = (_difftime NE .) KEEP = &idvar
_difftime);
BY &idvar;
auc = auc / _difftime;
RUN;
%MEND;

%auc (idvar = subject swab_type gene, dsname = rawdata3, timevar = day, yvar = log_cp_ml_d,
resultds = auc_result);
#####

```

9.2.1.2 Mixed effect Model for Repeated Measures (MMRM) of absolute change from baseline in viral load

Change from Baseline in Viral load via MMRM approach:

```
#####

```

```

ods exclude all;
ods output Diff0=diff0 classlevels=cl ConvergenceStatus=cs;
proc mixed data=viral_small_sim cl order=internal covtest;
  class usubjid trt01pn ady;
  model chg = antibs base base*ady trt01pn*ady / solution ddfm=Kenwardroger
  outpred=outpred1;
  repeated ady / type=un subject=usubjid;
  lsmeans trt01pn*ady / pdiff=control ("100" "&cutoffdays") obsmargins cl alpha=0.05
  slice=ady;
run;
ods exclude none;
#####

```

Where:

- usubjid = subject
- trt01pn = treatment arm (here numeric)
- ady = analysis day
- antibs = antibody status
- base = baseline viral load
- chg = change from baseline in viral load
- cutoffdays = day for analysis → 7 (primary analysis) or 28 (sensitivity analysis)

Note that the reference level in the code above (“100”) has to be adapted to the level used in the study.

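### For Group 2D viral load in the mITT set, the SAP's actual-treatment default contradicts the protocol's rule to analyse by randomised allocation

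*SAP*

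**What the plan says.** - **SAP 6.1 (Treatments)** gives the general rule: "All analyses will be based on the actual treatment the subjects received unless stated otherwise".
- **Protocol 8.1.1 (Analysis Populations, Group 2D)** separates two sets. The safety population is analysed as treated. For the mITT set it adds: "The evaluation is carried out strictly in accordance with the allocation by randomization".
- **Protocol 8.1.4** says of secondary and exploratory outcomes: "Endpoints will be evaluated mainly in the safety population (dose escalation phase) or in the mITT population", the latter being for Group 2D. It calls the time-weighted average change in viral RNA shedding the main efficacy analysis.
- **SAP 6.3** defines the mITT set: "This subject set includes all randomised subjects in the phase IIa part of the trial that received any amount of study drug", with a baseline and a second nasopharyngeal value in the first week. This says who is in the set, not in which arm each person is counted.
- **SAP 7.5.2.2.3** (nasopharyngeal viral load, phase IIa): "All evaluations for the first 7 days after drug administration will be done on the mITT set". No assignment rule follows.
- **SAP Table 6.2: 1** lists, as code C2, medication that does not match the randomised treatment. It excludes such participants from no analysis set.
- **SAP 4.2** lists three changes from the protocol: the sex subgroup, the day labels and the immune-cell endpoint. SAP 4.1 and 4.3 do not mention treatment assignment either.

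**The concern.** Group 2D is the only randomised comparison in the trial, and viral load over the first 7 days is its main efficacy analysis. The protocol fixes the arm at randomisation for that analysis. Read literally, the SAP regroups participants by what they received. Grouping as treated suits safety, exposure and PK. For an antiviral comparison it gives up the protection of randomisation whenever the reason for the mismatch is related to the participant's condition or tolerance of treatment.

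The rule also needs to be settled in advance. Group 2D is unblinded for the analysis after the last day 7 visit (protocol 5.9.6.1), and SAP 9.1.2 uses that analysis to inform further development. If the conflict is left for programming to resolve, the arm of a mismatched participant could be chosen with the allocation known.

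**Working it through.** No figure in the plan depends on the assignment rule, so the main check is a comparison of texts. Arithmetic then gives the scale.

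**Step 1: does any SAP text override the 6.1 default for this analysis?**
- SAP 6.3, mITT definition: membership only, no rule on arm.
- SAP 7.5.2.2.3, ANCOVA, MMRM and clearance rate: no rule on arm.
- SAP 9.2.1.2, MMRM sample code: trt01pn is defined only as the treatment arm, without saying planned or actual.
- SAP 4.1 to 4.3: nothing on assignment.

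The default therefore applies, and it is the opposite of protocol 8.1.1.

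**Step 2: can the two rules place a participant in different arms?** Yes. C2 cases stay in the mITT set, so the assignment rule decides their arm. A second route is an inference from the text. The protocol's mITT set requires inhalation and infusion, whereas the SAP's requires any amount of study drug. A participant randomised to inhaled plus intravenous DZIF-10c whose infusion was never started could be in the SAP set having received inhaled drug only. The SAP does not say in which arm that participant counts.

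**Step 3: scale.** The one design number used is 20 per arm (protocol 8.2). The 90% intervals printed there reproduce with p ± 1.645·√(p(1−p)/20):
- 20%: 5.3% to 34.7% (printed 5% to 35%)
- 25%: 9.1% to 40.9% (printed 9% to 41%)
- 30%: 13.1% to 46.9% (printed 13% to 47%)

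This confirms the arm size; the intervals do not depend on the rule.

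One participant is 1/20 = 5% of an arm. The documents give no count of mismatches, so take k = 0 to 3 as an assumption. Assume also that all 20 per arm are in the mITT set, that the effect is the same for everyone, and that mismatch is unrelated to prognosis.

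- *One-way*: k participants randomised to placebo receive one of the active regimens. The as-treated sizes of those two arms are 20 − k and 20 + k. Analysis by randomisation retains 1 − k/20 of the contrast between them.
- *Swap*: k pairs exchange treatment between the two arms. Sizes stay at 20 and 20. Analysis by randomisation retains 1 − 2k/20.

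| k | As-treated sizes (one-way) | Contrast retained, one-way | Contrast retained, swap |
|---|---|---|---|
| 0 | 20 / 20 | 100% | 100% |
| 1 | 19 / 21 | 95% | 90% |
| 2 | 18 / 22 | 90% | 80% |
| 3 | 17 / 23 | 85% | 70% |

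At k = 0 the rules coincide. For k of 1 or more they estimate different things. By-randomisation is somewhat diluted but keeps the randomised groups; as-treated avoids the dilution only if the mismatch is unrelated to prognosis.

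**The case against.** The strongest reply is that this is a wording conflict on a descriptive secondary endpoint that may have no effect.

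- Randomisation is central and web-based, and pharmacists receive assignments through that software (protocol 5.9.4 and 5.9.6).
- The proportion of participants with important deviations, C2 among them, is to be reported (SAP 6.2), so a mismatch would not be hidden.
- The primary endpoint is adverse events, analysed as treated under both documents.
- Group 2D is hypothesis-generating and not powered for viral load (protocol 8.2), and p-values are nominal (SAP 7.5).

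All of this stands. It limits the severity but does not reconcile the two sentences.

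Four stronger readings are tempting, and the documents do not support them.

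1. *All Group 2D efficacy endpoints are analysed as treated.* SAP 6.1 is only a default. For symptom resolution, SAP 7.6.2.5 takes the hazard ratio "between each of the two randomised treatment regimens that were assigned DZIF-10c and the placebo regimen", which can be read as an exception.
2. *Using treated-set populations for later viral load, oropharyngeal swabs, virus isolation and symptoms is an undeclared breach.* Protocol 8.1.4 prescribes mITT only as the main set, protocol 8.1.1 lets the SAP define further populations, and SAP 4.1 points to them. mITT membership rests on nasopharyngeal swabs, which is not a natural condition for the other endpoints. Choosing the treated set does not in itself undo randomisation; only the assignment rule could.
3. *The sample code contradicts the text.* The name trt01p may suggest planned treatment, but the SAP does not say so, and SAP 9.2 says the code has to be adapted. The code is silent on the point.
4. *The randomised comparison is already broken.* That would need an actual mismatch, and the documents report none.

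**Conclusion.** The contradiction holds for nasopharyngeal viral load in the Group 2D mITT set over the first 7 days (time-weighted average ANCOVA, MMRM and clearance rate). Protocol 8.1.1 requires the randomised arm, SAP 6.1 by default uses the treatment received, no exception is stated, and the departure is not declared. Its effect is zero if everyone received the randomised regimen. Otherwise each affected participant is 5% of an arm of 20. The number affected is unknown, and the range of 0 to 3 above is an illustration, not an estimate.

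This should be fixed before the Group 2D data are unblinded. It does not invalidate the plan: the primary endpoint is unaffected and the comparison is exploratory.

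**What to change.** Keep the SAP 6.1 default and add to it: *except that in Group 2D all mITT analyses and other between-arm antiviral and clinical efficacy analyses (viral load, virus isolation, hospitalisation or medical contacts, symptom resolution) use the randomised arm.* Repeat this in the mITT definition in SAP 6.3 and in SAP 7.5.2.2.3, and define trt01p and trt01pn in SAP 9.2 as the randomised arm for these models. Safety, exposure, ADA and PK stay by actual treatment.

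Adding an exception is safer than replacing the sentence with a list of analyses, which could leave ADA, demographic and phase I analyses with no stated rule. If the sponsor does intend actual treatment for viral load, SAP 4.2 should declare and justify the departure from the protocol.

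The cost is a few sentences and one variable definition, with no new data or analyses. The statistical price is the modest dilution shown above if a mismatch occurs, which the protocol's rule already accepts.
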